### 3.4. Criteria for Premature Withdrawal

Participants will be withdrawn from the study for the following reasons:

- Participants are no longer considered suitable for surgical lung resection by the MDT. Other treatment options may be considered more prudent such as radiotherapy or systematic anticancer treatment or best supportive care.
- The participant decides they no longer wish to be part of the study or have decided against surgical resection
- The research team decide it is unsafe for the participant to continue due to medical, safety and regulatory concerns. This includes adverse cardio-respiratory events relating to the patients physical conditioning as assessed by the cardiothoracic physiotherapists
- If the participant becomes lost to follow-up as deemed by the research team
- If the participant loses their capacity during the study period (including death)
- A significant increase in post-surgical mortality

Patients have the right to refuse study participation.

If a participant loses capacity to consent or withdraws consent, they will be withdrawn from the study. Identifiable data already collected with consent would be retained and used in the study. No further data would be collected or any other research procedures carried out on or in relation to the participant.

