## 1. Introduction

### 1.1. Background

Lung cancer is the most common cause of cancer-related deaths in Wales (1). Although surgical resection for early-stage lung cancer with curative intent remains the primary treatment, patients with significant smoking related underlying cardiopulmonary disease and impaired pulmonary function, dyspnoea, frailty and decreased activity levels are unfit for surgery and referred for alternative treatment (2,3). Secondly, individuals who proceed to lung resection, thoracic surgery and general anaesthesia may have direct effects on their respiratory system potentially leading to postoperative pulmonary complications (PPCs), which increases hospital morbidity, prolongs hospital length of stay (HLOS) impacts on the quality of life (QOL) of patients and adds to health-care costs (4). Our aim is to evaluate whether incorporating a breathing training device, POWERBreathe into the existing standardised thoracic prehabilitation program (Prehab) will optimise unfit patients physically for surgery, and following surgery reduce their risk of developing PPC's, reduce HLOS and improve QOL of patients and improve service outcomes (5).

The PRIMROSE study aims to compare two groups of patients referred for Prehab who have lung cancer treatable with surgery: (A) standard Prehab and training with the inspiratory muscle training (IMT) device; and (B) standard Prehab alone, in non-small cell lung cancer patients (NSCLC) undergoing lung resection surgery, with clear primary and secondary outcome measures.

One hundred and thirty-four patients will be recruited for the study (67 for each arm) and with an anticipated attrition rate of 25%, one hundred patients will finally be studied (6,7). With 134 recruited and an attrition rate of 25%, only 100 will remain (50 in each arm). The primary outcome measure tested will be the proportion of patients in each group experiencing postoperative pulmonary complications (PPC), which will be graded I-V using the Clavien Dindo Classification (8). PPCs will be broadly classified as minor (grade 1) and major complications (grade 2-5 where 5 is death). What we want to learn from this RCT study is whether IMT helps reduce grade  $\geq 2$  PPCs to either grade 1 or no complications and thereby help shorten the length of stay in hospital for patients undergoing lung resection surgery.

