## 1.2. Preclinical Data

[figure not shown]
Lung cancer treatment has complex and critical challenges as highlighted by The Welsh NHS Confederation (2015), the Welsh Government Parliamentary Review of Health and Social Care in Wales (2018) and A Healthier Wales (2018) (10,12). These include shifting demographics, an ever-ageing population and increased prevalence of complex and chronic conditions alongside fiscal constraints. For example, 63% of patients with lung cancer have chronic obstructive pulmonary disease (COPD), resulting in breathlessness and poor exercise tolerance and predispose surgical patients to post-operative pulmonary complications (PPC's) increased morbidity, longer hospital length of stays (HLOS) and mortality (4,13)

Smoking accounts for about 90% of all lung cancer cases (13). Patients with resectable NSCLC may have smoking related underlying cardiopulmonary disease causing significant dyspnoea (due to impaired or poor pulmonary function), impaired performance status (PS) and impaired levels of activity (LOA) (14,15). Loss of lung tissue in deconditioned NSCLC patients may grossly impair their postoperative ventilatory function, predisposing them to significant dyspnoea and cardiopulmonary complications. These patients are considered high-risk for surgery or inoperable and referred for radiotherapy, systemic anticancer treatment, or palliative care instead (2-4, 13-15). In Wales, an average of only 17% of patients undergo lung resection annually (16).

Of those individuals who proceed to lung resection, thoracic surgery and general anaesthesia may have direct effects on their respiratory system predisposing patients to PPCs, which increases hospital morbidity, prolongs HLOS and adds to health-care costs (4). PPCs in patients for thoracotomy and lung resection with chronic lung disease have been reported to be as high as 30% (4). Decreased lung expansion due to poor inspiratory muscle strength (respiratory muscle weakness) causes atelectasis and PPCs (4). Reduced respiratory muscle function along with reduced mucociliary function and bacterial proliferation promote colonisation of the respiratory tract by bacteria leading to pneumonia and acute respiratory distress syndrome with patients requiring intensive care treatment and longer HLOS, which

increase National Health Service (NHS) costs, places pressures on critical care beds and increases mortality (4).

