## Data collection

QoL data using EORTC QLQ-30 questionnaire will be collected at initial assessment (T0) and on completion of Prehab (T1) as final assessment, then post-surgery at discharge (T2) and at 1 month following surgery (T3).

Subjective outcome measures data include dyspnoea score, PS, thoracoscore, frailty index (FI), LOA and objective measures include 6-minute walk distance test (6MWD) at initial assessment (T0), after every two weeks in Prehab to assess for improvement, and finally at final assessment prior to participants proceeding to surgery (T1) (14,15,30). LOA, measured using the Borg scale of perceived exertion, will be recorded as sedentary, moderately active or active and supplemented by the 6MWD. The 6MWD will be performed using a 10m corridor instead of 30m (31). A 10 metre track along a flat corridor, will be used to measure the distance walked in metres within the 6 minutes. A 10m track was used in our previously published study and proved very effective. The American Thoracic Society guidelines state a distance of 30 metres (100 foot) should be used, however this is difficult practically. It is rare to find a 30-metre corridor in a hospital that is quiet and can allow a chair to be positioned for seated rests. A 10 metre track will be better from a health and safety point of view, as well as giving patient's privacy to focus on the self-paced walk test. These above outcome measures are already standard care for all Prehab patients (14,15).

Calculating the thoracoscore for each individual for lung resection in percentage describes the mortality risk of the individual for surgery. This is already standard operating procedure (SOP) for obtaining informed consent for lung resection surgery, and will be calculated for each participant (T0 and T1) (2,32).

The maximal inspiratory pressure (MIP) for both groups will be measured using a POWERbreathe device (Figure 2) at initial assessment (T0), on completion of Prehab (T1) and at discharge (T2). Measuring MIP is not standard practice for Prehab and will be an additional and essential outcome measure. It is required to assess the progress of each individuals improvement with the Prehab. Due consideration regarding IMT contraindications in patients to avoid harm or adverse events is included in our inclusion/exclusion criteria.

Following surgery, data on PPC's and HLOS will be collected by the researcher. This is standard practice for the prehab service.

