**Post-discharge assessment:** Our primary objective is to determine whether IMT prior to surgery with Prehab helps reduce PPC following surgery, which is up to the point of discharge from hospital (alive or dead). This is one time point. Hence, it is anticipated that all patients will complete the discharge assessment for complications. Thus, the study is not underpowered for the primary end point.

Mortality rates will be collected at discharge, 1 month, 3 months, and 365 days post-surgery.

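### Section 3.4 withdraws participants who lose capacity and bars further data on them, which contradicts the sections that need a complication record at discharge and mortality to one year for every patient

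*Protocol*

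**What the plan says.** Section 3.4 lists, among the reasons for withdrawing a participant, "If the participant loses their capacity during the study period (including death". Its closing paragraph gives the consequence: "If a participant loses capacity to consent or withdraws consent, they will be withdrawn from the study". Data obtained up to then are kept ("Identifiable data already collected with consent would be retained and used in the study"), but from that point "No further data would be collected or any other research procedures carried out on or in relation to the participant". Neither this section nor any other exempts temporary incapacity, the primary endpoint, mortality or routine hospital records.

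Other sections need those data:

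- Section 1.1 makes the proportion of patients with a PPC the primary outcome, graded I-V on Clavien Dindo: "PPCs will be broadly classified as minor (grade 1) and major complications (grade 2-5 where 5 is death".
- Section 2.4.1 (post-discharge assessment) runs the endpoint window to hospital discharge, whether the patient leaves alive or has died. It continues "Hence, it is anticipated that all patients will complete the discharge assessment for complications" and concludes from this that the primary endpoint is not underpowered. It also requires mortality at discharge, 1 month, 3 months and 365 days.
- Section 4.5 (Figure 6) marks complications and length of stay at T2 (discharge) only, and mortality at T2 to T5.
- Section 4.12 includes all patients, withdrawn ones among them, by intention to treat.
- Section 2.4.1 (data collection) says of the post-operative data: "Following surgery, data on PPC's and HLOS will be collected by the researcher. This is standard practice for the prehab service".

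**The concern.** Severe PPCs are among the events that can take away capacity. Section 1.2 describes such a course, with impaired respiratory function "leading to pneumonia and acute respiratory distress syndrome with patients requiring intensive care treatment and longer HLOS". A patient sedated and ventilated in intensive care cannot consent. If the 3.4 rule is applied to that patient, withdrawal comes before T2, the only scheduled complication record. The final PPC grade, the length of stay and any later death would then go uncollected, so the outcome would cause its own absence.

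This differs from pre-operative attrition, for which the plan allows 25%. Intention to treat keeps the patient in the analysis set but cannot supply an outcome that nobody was allowed to collect. The claim in 2.4.1 about power rests on a complete discharge record, and the harm comparison in 7.3 uses the same complication and mortality data.

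**Working it through.** **The text, step by step**

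1. Trigger: loss of capacity, with no qualification as to duration or cause (3.4).
2. Consequence: withdrawal, and no further data (3.4).
3. Scheduled complication and length-of-stay record: T2 only (Figure 6).
4. Therefore a patient who loses capacity between surgery and T2 has no permitted T2 record. Section 2.4.1 expects that record for everyone, and 4.12 analyses everyone. Staff who follow 3.4 cannot satisfy 2.4.1, and staff who follow 2.4.1 breach 3.4.
5. Death: the sentence barring data names loss of capacity and withdrawal of consent only. Death enters through the bullet's parenthesis. Classing it as withdrawal conflicts with 1.1 (grade 5), 2.4.1 and 4.5 (mortality time points), 7.3 (mortality as a safety endpoint) and 5.1.2, which itself notes that death is an outcome.

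**The plan's own figures**

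- Recruitment: N/(1 - d) = 50/(1 - 0.25) = 66.7, so 67 per arm and 134 in total. This reproduces.
- 50 per arm: the readable text gives the control rate (36.7%), two-sided alpha 0.05 and 80% power, but no intervention rate (Figure 5 is not shown). Solving backwards gives an intervention rate of 12.6-12.8% (pooled variance) or 13.2-13.3% (unpooled). I use 13% as an assumption.

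**Illustration**

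Assumed: a share s of PPC patients loses the endpoint record, equal in both arms, with 50 per arm. Expected PPCs are 50 x 0.367 = 18.35 in control and 50 x 0.13 = 6.5 with inspiratory muscle training (IMT).

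- If dropped: n' = 50(1 - ps) and q = p(1 - s)/(1 - ps).
- If counted as no PPC: n' = 50 and q = p(1 - s).
- Power = Φ{[|q1 - q2| - 1.96 √(q̄(1 - q̄)(1/n1 + 1/n2))] / √(q1(1 - q1)/n1 + q2(1 - q2)/n2)}, where q̄ is the pooled proportion.

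With s = 0: q̄ = 0.2485, and the numerator is 0.237 - 1.96 x 0.0864 = 0.0676. Dividing by 0.0831 gives 0.813, so power is 79%.

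With s = 20%, dropped: n1 = 46.3, n2 = 48.7, q1 = 0.2936/0.9266 = 0.317 and q2 = 0.104/0.974 = 0.107. Power is 72%.

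| s | Power, dropped | RR, dropped | Power, counted as no PPC | RR, counted as no PPC |
|---|---|---|---|---|
| 0 | 79% | 0.354 | 79% | 0.354 |
| 5% | 78% | 0.350 | 76% | 0.354 |
| 10% | 76% | 0.346 | 73% | 0.354 |
| 20% | 72% | 0.337 | 67% | 0.354 |
| 30% | 67% | 0.328 | 59% | 0.354 |

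In the last column the factor (1 - s) cancels.

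**Unequal loss, dropped**

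- 20% of control and 10% of IMT PPC patients: RR 0.374, power 66%.
- 10% of control and 20% of IMT PPC patients: RR 0.311, power about 80%.

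The relative risk, which the plan names as its effect measure, can move either way or stay put.

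**The case against.** The strongest defence is that several sections show an intent to count these patients (2.4.1, 4.5, 4.12, 7.3), so 3.4 is loose drafting that staff would not apply to a ventilated patient. Taken literally, general anaesthesia would withdraw every operated patient, which cannot be meant. This stands in part: the intended reach of the capacity rule is unclear. But no section overrides the explicit bar, and none says where temporary incapacity stops counting.

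Nor is everything lost. Data already collected are kept. Section 2.1 expects contemporaneous collection, 2.4.1 has PPC data gathered after surgery as standard practice, and 6.2 puts non-serious adverse events in the case report form. A pneumonia noted before sedation would survive, so PPC occurrence may be known even where final grade and length of stay are not. This stands and limits the point.

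The capacity rule is also a legitimate participant protection, and the consent pages are not available, so they may already permit continued use of records. That stands too. However, IMT is given only before surgery (4.4), so withdrawal after the operation stops no IMT.

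A reader might infer three stronger things that the documents do not support:

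- That all deaths go unrecorded. The data bar does not name death, and a death logged as a reason for leaving is still recorded. Only deaths preceded by incapacity are exposed.
- That nearly all of the most severe PPCs are lost. No share is given anywhere.
- That the treatment effect must shrink. Equal proportional loss leaves the relative risk unchanged or moves it further from 1, and unequal loss can move it either way.

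**Conclusion.** The contradiction is real. Section 3.4, as written, stops collection of data that 2.4.1, 4.5 and 4.12 require, and for patients whose PPC leads to incapacity before discharge the missingness depends on the outcome. What is at risk is the final PPC grade, length of stay and later mortality of those patients, and PPC occurrence only where it was not recorded first. PPCs without incapacity are untouched.

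The size is unknown. If 5-30% of PPC patients in both arms lost the endpoint altogether, power would fall from about 79% to 78-67% (dropped) or 76-59% (counted as no PPC). This rests on an assumed 13% IMT rate, an assumed share and 50 per arm. At 5-10% the loss of power is modest. No direction of bias should be claimed. The point still warrants an amendment, because outcomes never collected cannot be recovered at analysis.

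**What to change.** Reconcile 3.4 with 2.4.1, 4.5 and 4.12:

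- Delete the parenthesis that counts death as loss of capacity, and state that death is an outcome, not a withdrawal.
- State that loss of capacity ends research-only procedures (such as inspiratory pressure measurement and the quality-of-life questionnaire). PPC occurrence and grade, length of stay and mortality already held in routine records continue to be collected to the planned time points, as far as consent given at enrolment and ethics approval allow.
- Say whether temporary peri-operative incapacity falls under the rule.
- Check first whether the consent form already covers continued access to records. If not, add a line.

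The cost is a protocol amendment, possibly a consent-form amendment, and ethics review. No extra visits are needed, since 2.4.1 says PPC and length-of-stay data are already collected as standard practice.

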## 4. Study Procedures

### 4.1. Informed Consent Procedures

It is the responsibility of the research team, who have been appropriately trained cardiothoracic physiotherapists and technicians (as documented in the research delegation log) to obtain written informed consent from each subject prior to any study participation. The research team will be trained by the PI, on when to approach a potential participant, what information they should provide (written and verbally), and how to record details of the consent decision.

Informed Consent Forms (ICF) and Patient Information Sheets (PIS) will be available in large print, with clear written language and available in English and Welsh.

Additionally, the research team will provide adequate explanation of the aims, methods, anticipated benefits and potential hazards of the study.

If a participant wishes to speak to a cardiothoracic surgeon, the research team will organize a telephone discussion. If necessary, a second consent visit should be arranged and the research team will not take consent at this time.

The patient should be given at least 24 hours to consider giving their consent for the study. If for any reason, less than 24 hours is given, the reasons should be documented, along with justification for this decision. The date that the PIS is given to the patient will be documented within the patient's notes to ensure that a minimum of 24 hours has been provided.

The PI or other member of the research team will explain to the potential participant that they are free to refuse any involvement within the study or alternatively withdraw their consent at any point during the study and for any reason.

Once a patient has consented to take part in the trial research study a research label should be attached to their hospital case notes to indicate involvement.

All relevant research related documentation should be filed in the participants physiotherapy notes. This will consist of a copy of the ICF and PIS .Written records of each research event for example randomization, trial visits or follow up phone calls will be recorded within the physiotherapy notes.

If there is any further safety information, which may result in significant changes in the risk/benefit analysis, the PIS and ICF will be reviewed and updated accordingly. All subjects that are actively enrolled on the study will be informed of the updated information and given a revised copy of the PIS/ICF in order to confirm their wish to continue on the study.

The informed consent process will not cease once the ICF has been signed; the practice of giving information about the research project to participants will be an ongoing process at each contact. Ongoing verbal consent will be confirmed and documented as part of each research-contact by the research team.

## 4.2. Screening Procedures

For each patient referred to Prehab, the diagnosis and stage of lung cancer will be validated with the data documented on the Welsh Clinical Portal system by the CI and research team. This is standard practice in the staging and management of lung cancer. The International Association for the Study of Lung Cancer (IASLC) lung cancer staging system, 8th edition, will be used for pre-treatment clinical staging of patients with suspected or diagnosed lung cancer (33).

## 4.3. Randomisation Procedures (if applicable)

Participants will be randomised 1:1 to either the intervention or control group without stratification using an online randomisation service, 'Sealed Envelope' ([wwwsealedenvelope.com](http://wwwsealedenvelope.com)) (34).

## 4.4. Schedule of Treatment for each visit

On initial face-to-face assessment, conducted within 5 working days of receiving the referral for Prehab, the research team will provide participants with participant information sheet and informed consent form. Informed consent to participate will be obtained. Patients can bring carers to the face-to face assessment if they wish.

**Control group:** The control group will receive a standard Prehab protocol.

**Standard Prehab protocol** is described in our previous pragmatic study published in the Lancet journal *Journal of Clinical Medicine* (15). Prehab will be provided to participants over 2–4 weeks with supervised once weekly sessions ~~with supervised two weekly sessions~~ of 70 minutes each, along with exercises for patients to carry out at home. Three weeks is an anticipated average based on published data and urgency to proceed to surgery as cancer can grow and become inoperable by six weeks. This area is much debated in the Prehab literature. Our aim is to ensure as many patients benefit with Prehab followed by lung resection surgery as possible, with broader health benefits to patients and a positive impact on their quality of life. Our previous study showed that patients can be physically optimised safely in as little as two weeks (15). However, for patients who may be slower to respond there is scope in our program for a more prolonged course of Prehab if required.

Outcome measures will be collected every two weeks on the Prehab programme by the research team, which is standard practice. As patients become eligible, they will withdraw from Prehab and proceed to surgery once a surgical date is confirmed. Management of individuals deemed unfit for surgery will be discussed at the individuals' local lung cancer MDT for consideration of alternative treatment options namely, radiotherapy, systemic anti-cancer treatment or palliative care.

**Respiratory muscle training and breathing exercises.** Both groups will receive incentive spirometry devices pre operatively. Participants will be encouraged to practice and train with the spirometer device three times daily, so can use the spirometer effectively post operatively. This is standard care as spirometers aid lung volumes and removal of secretions post operatively.

**Cardiovascular exercises:** namely, stationary cycle ergometry and upper and lower limb resistance exercises will be performed, whilst monitoring the heart rate, blood pressure and oxygen saturations (15). The rate of perceived exertion (RPE) will be measured using the Borg breathlessness scale and used twice at every session to measure the intensity at which each patient is working and guide them to increase or decrease their effort as required.

**Home Exercise Program (HEP):** individualised home exercise programme includes daily walking plan and stair climbing exercise (15). Training enabling them to maintain activities of daily living following surgery. The HEP will be continued following discharge after surgery.

**Health education and smoking cessation advice** will be provided to all current smokers prior to surgery and support following surgery (15). Where necessary nicotine replacement therapy will be provided.

**Intervention group:** The intervention group will receive IMT in addition to a standard Prehab protocol (as above). An MIP in cmH2O, obtained at or greater than 1.5 seconds will be recorded, and the highest MIP of 3 valid breaths will be used as baseline. The IMT pressure in cmH2O will be set initially at 40% of the patients MIP. Participants will be taught to use the device in an upright position and instructed to perform six sets of six breaths with the resting times between each set of breaths reducing from 60 seconds, to 45 seconds, to 30 seconds, to 15 seconds, to 5 seconds. IMT will be used twice-daily preoperatively in the intervention group and not post operatively. Training load intensity on the IMT will be

increased preoperatively by the patient according to the rate of perceived inspiratory effort, on a modified Borg scale.

